return for their regularly scheduled clinical assessments at 12 and 24 months as outlined above, at which efficacy and quality of life will be assessed along with concomitant medications. New AEs will be collected for 4 weeks post last dose and followed up for 12 weeks, or until resolution, whichever comes first. AEs relating to study procedures will be collected until the end of study participation. (revised per Amendment 05) However, subjects who discontinue study drug early are not considered to have ‘completed’ the study as a final Subject Disposition.

The primary reason for discontinuation and all other reason(s) contributing to the subject’s discontinuation from study drug(s) should be collected on the ED from study drug eCRF page. In addition, the date of last dose of study drug(s) will be recorded on the Study Drug Dosing eCRF page. If a subject discontinues study treatment and the study at the same time, the end-of-study procedures (Final Visit) will be followed (see [Section 9.5.5](#)).

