Day	1	15	29	57	85	183	274	365	456	547	638	729		757	813	
Week	1	3	5	9	13	27	40	53	66	79	92	105		109	117	
Weeks elapsed since 1st dose	0	2	4	8	12	26	39	52	65	78	91	104		108	116	
Nominal months elapsed since 1st dose	0		1	2	3	6	9	12	15	18	21	24		25	27	
Procedures/ Assessments																

- b: Subjects who discontinue taking study drug prematurely for any reason will undergo an ED Visit within 7 days of their last dose of study drug. In addition, Follow-up Visits will be scheduled 4 and 12 weeks after the last dose of study drug (Visit 14 and Visit 15, respectively). Subjects who discontinue study drug before reaching 12 months of treatment will also be asked to return to the clinic for a 12 month clinical assessment and then again at 24 months. Subjects who discontinue treatment between 12 and 24 months of treatment will be asked to return to the clinic for a 24 month clinical assessment. Subjects who discontinue early from study drug are considered “on study” as long as they continue to return for their clinical assessments at 12 and 24 months as outlined above, at which efficacy (MMSE, CDR, ADAS- cog14) and quality of life (EQ-5D, QOL-AD and Zarit’s Burden Interview) will be assessed along with concomitant medications. New AEs will be collected for 4 weeks post last dose and followed-up for 12 weeks, or until resolution, whichever comes first. If >4 weeks post last dose only AEs relating to study procedures will be collected. These 12 and 24 month clinical assessment visits do not need to be attended if they fall within 8 days (visit window) after the ED Visit or within ±8 days of either of the Follow-up Visits (Visit 14 and Visit 15).

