9.7.1.1.2 SECONDARY ENDPOINTS

The key secondary endpoints of the study are as follows (revised per Amendment 05):

- Change from baseline in ADCOMS at 24 months in the combined studies
- Change from baseline in amyloid PET SUVR at 24 months for brain amyloid levels in the combined studies
- Change from baseline in amyloid PET SUVR at 24 months for brain amyloid levels in the individual studies

The other secondary endpoints of the study are as follows (revised per Amendment 05):

- Change from baseline in the CDR-SB at 24 months for subjects enriched by baseline PET SUVR, eg, between 1.2 and 1.6, in the combined studies
- Change from baseline in the ADCOMS at 24 months for subjects enriched by baseline PET SUVR, eg, between 1.2 and 1.6, in the combined studies
- The rate of change over time (mean slope) based on CDR-SB score over 24 months in the combined studies
- Time to worsening of CDR scores by 24 months (eg, the worsening of global CDR score is defined as an increase from baseline by at least 0.5 points on the global CDR scale on 2 consecutive scheduled visits at which global CDR is undertaken) in the combined studies

- Time to conversion to dementia by 24 months for subjects who were not clinically staged as dementia at Baseline based on clinical diagnosis in the combined studies
- Change from baseline in CDR-SB at 27 months (ie, 24 months of treatment plus 3 months posttreatment follow-up) in the combined studies
- Change from baseline in ADAS-cog14, MMSE, and FAQ at 24 months in the combined studies
- Change from baseline in ADAS-cog14 Word List (immediate recall and delayed recall) at 24 months in the combined studies

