9.7.1.6.1 PRIMARY EFFICACY ANALYSIS

The primary analysis will be based on an intent to treat philosophy without regard to adherence to treatment. The primary analysis of the change from baseline in CDR-SB at 24 months will be performed to compare elenbecestat 50 mg per day versus placebo using a linear mixed effects model for repeated measures (MMRM) on the FAS. The MMRM model will include fixed effects of treatment group, visit, treatment group by visit interaction, baseline CDR-SB, baseline CDR-SB by visit interaction, and randomization stratification variables (ie, region [7 levels], clinical dementia [yes, no], and concurrent AD medication use at randomization [Visit 2] [yes, no]). *ApoE4* status may be included in the model if appropriate. (revised per Amendment 05) An unstructured covariance matrix will be employed to model the covariance of within subject effect; if MMRM fails to converge then a covariance structure with fewer parameters from the following list will be employed according to the prespecified order in the list until the MMRM converges. The list of covariance structure will include Heterogeneous Toeplitz, Toeplitz, Heterogeneous Compound Symmetry, and Compound Symmetry. This primary analysis will include all observed post baseline data of the change from baseline in CDR-SB without imputation of missing values. The treatment effect for elenbecestat versus placebo will be compared at

24 months based on MMRM model. The LS means and difference in LS means between elenbecestat treatment group and placebo, and corresponding 95% CI will be presented.

The null hypothesis is that there is no difference in the mean change from baseline in CDR-SB at 24 months between elenbecestat 50 mg per day and placebo. The corresponding alternative hypothesis is that there is a difference in the mean change from baseline in CDR-SB at 24 months between elenbecestat 50 mg per day and placebo.

The primary analysis will be repeated to minimize the impact of change in concomitant AD medications where efficacy data after initiation of new AD medications and increase of current AD medications will be censored.

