Time to worsening of CDR scores by 24 months will be analyzed on the FAS using Cox regression model for treatment effect adjusting for randomization stratification factors. ApoE4 status may be included in the model if appropriate. (revised per Amendment 05) Time to worsening of a CDR score is defined as time from randomization to worsening of the CDR score (ie, the first worsening in 2 consecutive scheduled visits). For subjects whose CDR scores have not worsened by the end of the Treatment Period of the Core Study, the time to worsening of the CDR score will be censored at the date of last CDR assessment for these subjects.

Time to conversion to dementia for subjects who were not clinically staged as dementia at Baseline based on clinical diagnosis will be analyzed on the FAS using Cox regression model for treatment effect adjusting for randomization stratification factors. ApoE4 status may be included in the model if appropriate. (revised per Amendment 05) Proportion of subjects with dementia diagnosis at 24 months will be estimated using Kaplan—Meier method based on time to conversion to dementia based on clinical diagnosis. Time to conversion to dementia for subjects who were not clinically staged as dementia at Baseline based on clinical diagnosis is defined as time from randomization to conversion to dementia based on clinical diagnosis. For subjects without clinical dementia by the end of study, the time to conversion to dementia based on clinical diagnosis will be censored at the date of last dementia diagnosis.

The other continuous secondary efficacy endpoints as defined above will be analyzed using the same MMRM model as the primary efficacy analysis to compare elenbecestat 50 mg per day versus placebo on the FAS, using baseline value corresponding to the response variable in the model.

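### Table 5 footnote b leaves the FAQ out of the month-12 and month-24 return visits of treatment discontinuers, so its month-24 analysis must extrapolate where CDR, MMSE and ADAS-cog14 are observed

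*Protocol*

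**What the plan says.** Subjects who stop drug before month 12 are asked back at months 12 and 24. For later stoppers the footnote says: "Subjects who discontinue treatment between 12 and 24 months of treatment will be asked to return to the clinic for a 24 month clinical assessment". It then lists what is done at those visits, "efficacy (MMSE, CDR, ADAS- cog14) and quality of life (EQ-5D, QOL-AD and" the Zarit interview, together with concomitant medications. The list carries no wording to mark it as examples.

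Section 9.3.3 describes the same visits more broadly, as ones "at which efficacy and quality of life will be assessed along with concomitant medications", and Section 9.5.5 uses similar wording. Section 9.5.1.3.1 places the FAQ among the efficacy scales. The Table 5 grid schedules the FAQ at Visits 9 and 13, at the ED visit and at follow-up Visits 14 and 15.

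Section 9.7.1.1.2 names as an other-secondary endpoint "Change from baseline in ADAS-cog14, MMSE, and FAQ at 24 months in the combined studies". Section 9.7.1.6.2 states the method: "The other continuous secondary efficacy endpoints as defined above will be analyzed using the same MMRM model as the primary efficacy analysis", on the FAS. For the primary analysis, Section 9.7.1.6.1 says: "The primary analysis will be based on an intent to treat philosophy without regard to adherence to treatment", using all observed post-baseline data.

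A further other-secondary endpoint is "Time to conversion to dementia by 24 months for subjects who were not clinically staged as dementia at Baseline". It rests on staging every 3 months and a Cox model that censors subjects at their last diagnosis. Staging is also absent from the footnote list.

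**The concern.** The return visits exist so that subjects who stop drug still contribute efficacy data at months 12 and 24. Under footnote b they do so for the CDR, MMSE and ADAS-cog14. For the FAQ they do not, although it is declared for the same time point and analysed with the same model on the same set.

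The month-24 FAQ comparison would then depend on an untestable assumption: that subjects who stopped drug go on as the model predicts from their observed FAQ values. For the other scales, the subjects who return supply the values directly. Because this concerns data collection, no analysis plan can recover the values afterwards.

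The protocol also gives the FAQ weight. Section 9.2.3 regards it as a better guide to clinical meaningfulness than cognitive change. For dementia conversion, the lack of staging at these visits means that 24-month status is unknown even for discontinuers who attend.

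**Working it through.** **1. The texts side by side.** Sections 9.3.3 and 9.5.5 promise efficacy with no list. Section 9.5.1.3.1 counts the FAQ as efficacy. Footnote b names three efficacy scales, and the FAQ is not one of them. The footnote is therefore narrower than the body text. Nothing in the body text adds staging by name to these visits.

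**2. What a discontinuer contributes.** Visits 14 and 15 fall 4 and 12 weeks after the last dose.
- Stop at week 26: the last FAQ is at week 26 + 12 = 38. CDR, MMSE and ADAS-cog14 are also taken at weeks 52 and 104. The gap from the last FAQ to month 24 is 104 − 38 = 66 weeks.
- Stop at week 92: Visit 15 falls at week 92 + 12 = 104. The footnote waives the return visit when it lies within 8 days of Visit 14 or 15, and Visit 15 includes the FAQ. Nothing is lost.

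The loss therefore falls on earlier stoppers and concerns the period beyond about 12 weeks off drug.

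**3. The plan's own sample size.** Inputs from Section 9.7.2: placebo change 1.46, SD 2.05, 25% reduction, 30% dropout, 90% power, two-sided 0.05.
- Difference = 0.25 × 1.46 = 0.365.
- n per arm = 2 × (1.960 + 1.282)² × 2.05² / 0.365² ≈ 663.
- After dropout: 663 / 0.70, rounded up to 948 per arm, 1896 in total, against the stated 1900.
- With 665 evaluable per arm (950 × 0.70), power is 90.1%.

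The figure reproduces. It rests on CDR-SB, which footnote b does collect, so adding the FAQ changes neither the sample size nor the power.

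**4. How many subjects.** The protocol gives no discontinuation rate. Reading the 30% dropout as drug discontinuation (an assumption) gives 1900 × 0.30 = 570. If a share r of them returns (assumed 25%, 50% or 75%), then 570r = 143, 285 or 428 subjects have month-24 CDR but no FAQ from that visit. At 10% or 20% discontinuation the pool would be 190 or 380.

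**5. Precision.** If only month-24 values counted, the ratio of standard errors with and without the extra FAQ would be √(1330 / (1330 + 570r)) = 0.950, 0.907 and 0.870, a reduction of 5%, 9% and 13%. MMRM also uses earlier FAQ values, so these are upper bounds. As an illustration, assume a correlation of 0.7 with an earlier FAQ available in everyone, so that variance is proportional to 0.49/1900 + 0.51/n:
- n = 1330: 0.000641
- r = 50%, n = 1615: 0.000574, and √(0.000574 / 0.000641) ≈ 0.946, a reduction of about 5%
- r = 25% and 75%: ratios 0.971 and 0.924, reductions of about 3% and 8%

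**6. Bias, as illustration only.** Suppose a share p discontinues, loses a fraction f of the drug effect, and the model carries the on-drug course forward. The estimate then exceeds the effect regardless of adherence by 1/(1 − pf) − 1.
- p = 10%: 3% (f = 0.25) to 11% (f = 1)
- p = 30%: 8% (f = 0.25) to 43% (f = 1)

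The documents give no value for f. The FAQ at Visits 14 and 15 would temper the extrapolation. Collecting the FAQ at the return visits corrects the estimate only through those who attend.

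**The case against.** The best defence is that the FAQ may already be due. Section 9.3.3 treats the returns as regularly scheduled month-12 and month-24 assessments, footnote a gives them the windows of Visits 7 to 13, and the Visit 9 and 13 columns include the FAQ. On that reading the parenthesis in footnote b is loose drafting. This stands as far as it goes: the document is inconsistent rather than settled against the FAQ. But the explicit list is in the schedule that sites work from, so the conflict needs resolving.

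A reader might infer more than the text supports:
- **That the FAQ becomes an on-treatment result.** It does not. The FAQ is taken at ED and Visits 14 and 15. Staging is taken at ED and, as far as the extracted table shows, at Visit 15. About 12 weeks off drug are covered.
- **That function goes unmeasured off drug.** Section 9.2.1 describes the CDR-SB as having cognitive and functional components, and the CDR is collected. The FAQ is the only dedicated functional scale, not the only source on function.
- **That an intent-to-treat commitment is broken.** That sentence is written for the primary analysis. It reaches the FAQ by inference from the shared model, and conversion only through use of the FAS.
- **That 570 subjects are affected.** The 30% is an allowance for subjects not evaluable on month-24 CDR-SB. A discontinuer who returns for the CDR is evaluable and need not be among them.
- **That adding staging at months 12 and 24 repairs the conversion analysis.** Staging is otherwise 3-monthly. Yearly records entered as exact dates would place discontinuers' conversions late, in a way tied to stopping drug.

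**Conclusion.** The point holds in limited form. Footnote b is narrower than Sections 9.3.3 and 9.5.5. If followed as written, it yields month-24 CDR, MMSE and ADAS-cog14 from returning discontinuers but no FAQ beyond about 12 weeks after the last dose. The month-24 FAQ estimate then relies on missing-at-random extrapolation where the other scales use observed off-drug values. Subjects who stop so late that Visit 15 falls at or near month 24 lose little or nothing.

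The size cannot be fixed from the protocol. The counts of 143 to 428 assume that all dropout is drug discontinuation and that 25% to 75% return. The 5% to 13% precision gain is a ceiling. The bias range depends wholly on assumed loss of effect. The FAQ and conversion are other-secondary endpoints outside the sequential key-secondary testing, and the primary endpoint, ADCOMS and the sample size are untouched. The correction is still worth making, because it is cheap and the values cannot be recovered later.

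**What to change.** Add the FAQ to the assessments in Table 5 footnote b for the month-12 and month-24 return visits. Name the same list in Sections 9.3.3 and 9.5.5, and state that these records enter the FAS MMRM for the FAQ.

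Record disease staging at the same visits so that 24-month dementia status is known for discontinuers who attend. Because these records are much sparser than the 3-monthly schedule, analyse conversions first seen there as interval-censored, or use them in a sensitivity analysis, rather than entering them as exact dates in the Cox model.

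The cost is one 10-item study-partner questionnaire, for which telephone contact is already allowed, and one staging decision using the central review already in place. No visit is added. The remaining drawback is coarser conversion dates for discontinuers than for subjects still on the regular schedule.

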9.4.5 Selection and Timing of Dose for Each Subject

Elenbecestat is administered orally, QD, in the morning with or without food. Study treatment will begin on Day 1 following randomization and will continue for 24 months.

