9.5.1.3.3 CEREBROSPINAL FLUID SAMPLING

Amyloid CSF is 1 of the 2 methods available at screening to determine subject eligibility for the study. (revised per Amendment 02) Subjects who undergo the eligibility CSF sample collection or who consent to the CSF longitudinal substudy will be encouraged to stay at the site after completion of LP for medical observation. CSF sample(s) will be collected by LP (gravity drip method only) after fasting (preferred), or at least 2 hours after the most recent meal.

CSF samples at Visit 13 should be collected while the subject is still on the study drug and before the other visit assessments. All ED CSF samples need to be taken no later than 7 days after the last dose of study drug. All CSF samples should be taken at approximately the same time of day as at the Screening Visit. (revised per Amendment 05)

Subjects who provide a CSF sample at Screening for amyloid eligibility purposes, but did not initially consent to the CSF longitudinal substudy may provide consent to the CSF longitudinal substudy at any point in time up to the CSF procedure at Visit 13 (or ED). INR results should be reviewed for subjects who consent to provide a CSF sample and are on concomitant anticoagulation/antiplatelet therapy, before LP; if they are assessed by the investigator to be at risk for bleeding, they are to be excluded from CSF collection. (revised per Amendment 01)

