- o: For those subjects who consent to the longitudinal CSF substudy, CSF should be collected at the same time of day for each assessment, preferably fasting or at least 2 hours post meal. For those subjects who consent to CSF and amyloid PET eligibility assessments, the 2 assessments should be separated by at least 48 hours between the 2 procedures. For these subjects, a positive amyloid result is needed for only 1 of the procedures to confirm eligibility (ie, even if 1 of the 2 results is negative for amyloid, the subject would still be eligible under the other, positive result). For subjects who are approved for rescreening, the CSF need not be repeated for eligibility if confirmed amyloid positive during the original screening procedure. A gravity drip collection method must be used. Subjects will be encouraged to stay at the site after completion of LP for medical observation. (revised per Amendments 04 and 05).
- p: Subjects receiving concomitant anticoagulation/antiplatelet therapy should have prothrombin time and INR (derived from prothrombin time) before LP; if they are assessed by the investigator to be at risk for bleeding, they are to be excluded from CSF collection. (revised per Amendment 01)

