- w: Two plasma PK samples will be obtained: 1 sample at predose (trough) and another sample 1 to 6 hours postdose at Visits 3, 4, 6, 7, 9, and 11 and another sample 4 to 8 hours postdose at Visit 13 (or ED). Therefore, subjects or their study partners must be instructed not to take their study drug at home on the day the PK sampling is performed. Instead, subjects will take the study drug at the clinic after collection of the predose PK sample. At Visit 13 (or ED), the trough PK blood sample should be collected shortly before or after completing the LP for subjects participating in the CSF substudy. If the study drug is temporarily suspended, postdose PK samples will not be required. If at an ED Visit, the subject has already stopped study drug, postdose

Table 5 Schedule of Procedures/Assessments in Study E2609-G000-302 (Revised per Amendments 04 and 05)

Phase	Randomization														
	Treatment												Follow-Up		UN Visit ^d
Visit ^a	2	3	4	5	6	7	8	9	10	11	12	13	ED ^b	14 ^c	
Day	1	15	29	57	85	183	274	365	456	547	638	729		757	813
Week	1	3	5	9	13	27	40	53	66	79	92	105		109	117
Weeks elapsed since 1st dose	0	2	4	8	12	26	39	52	65	78	91	104		108	116
Nominal months elapsed since 1st dose	0		1	2	3	6	9	12	15	18	21	24		25	27
Procedures/ Assessments															

PK samples are not required.

- x: PD and exploratory biomarker blood samples should be collected at fasting or at least 2 hours after the most recent meal and, as far as is feasible, samples should be taken at the same time of day at all visits. Samples should be taken predose at Visits 2, 3, 4, 6, 7, 9, 11, 13 (or ED), 14, and 15. (revised per Amendments 02 and 03)

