- y: For subjects who consent to participate in the CSF longitudinal substudy. Visit 13 (or ED) also includes blood PK and PD assessments and so the subject will be dosed at the clinic on these days. A CSF sample will be collected by LP between 4 and 8 hours postdose and at the same time of day as the subject's Screening LP (±1 hour). The CSF sample will be taken with the subject fasting (preferred) or at least 2 hours after the most recent meal. A gravity drip collection method must be used. If performed on the same day as the cognitive tests, the LP will be performed after the cognitive tests; the subject should rest and drink some fluid to hydrate after the cognitive tests and before the LP. Subjects will be encouraged to stay at the site after completion of LP for medical observation. The CSF sample will not be taken at the ED Visit if this visit occurs within 39 weeks of treatment or 3 months of a previous CSF sample. If at an ED Visit, the subject has already stopped study drug, then no dosing will take place, but the CSF sample will still be collected unless it was already collected within the past 3 months. Subjects receiving concomitant anticoagulation/antiplatelet therapy should have prothrombin time and INR (derived from prothrombin time) before LP; if they are assessed by the investigator to be at risk for bleeding, they are to be excluded from CSF collection. Note that subjects who are assessed by both amyloid PET and CSF are required to wait for a minimum of 48 hours between the 2 procedures. (revised per Amendment 01)
- z: Subjects reporting AEs relating to abnormal dreams, nightmares, or sleep terror will be questioned on the nature, frequency, and impact of these events.
- aa: AEs that may signal drug abuse potential require a more detailed follow-up through completion of a specific eCRF form (Possible drug abuse potential form/ questionnaire). Similarly, AEs reported during the first 4 weeks following the last dose of study drug that might indicate physical dependency also require a more detailed follow-up through completion of the same eCRF form. Categories and examples of AEs indicating signals of possible drug abuse are provided in [Appendix 3](#) and a more comprehensive list is provided in the eCRF Completion Guidelines. (revised per Amendments 01 and 03)

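### The two timing windows for the on-treatment lumbar puncture can both be met only if the Screening puncture was 3 to 9 hours after the planned clinic dose time, and the protocol does not require this

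*Protocol*

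**What the plan says.** Table 5 footnote y (Section 9.5.2.1) sets two conditions on the LP at Visit 13 or early discontinuation (ED). It reads: "A CSF sample will be collected by LP between 4 and 8 hours postdose and at the same time of day as the". The reference for the clock match, and its tolerance, are then given as "Screening LP (±1 hour"). Table 9 footnote k in Appendix 5 sets the same two conditions for Visit 24 or ED of the Extension Phase.

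The dose that starts the postdose clock is also constrained:
- Section 9.4.5: "Elenbecestat is administered orally, QD, in the morning with or without food".
- Table 5 footnote y: "Visit 13 (or ED) also includes blood PK and PD assessments and so the subject will be dosed at the clinic on these days".
- Table 5 footnote w bars dosing at home that day and adds: "Instead, subjects will take the study drug at the clinic after collection of the predose PK sample".

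The Screening LP has no such constraint. Table 4 footnote o says only that "CSF should be collected at the same time of day for each assessment, preferably fasting or at least 2 hours post meal". Table 4 footnote j fits the Screening blood draw to the planned LP time, not the LP to anything else. Section 9.5.1.3.3 states the clock match more loosely than footnote y, as approximately the same time of day with no hour limit. It also lets a subject who gave CSF for eligibility join the longitudinal substudy "at any point in time up to the CSF procedure at Visit 13" (or ED).

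One exception is written in. If the subject has already stopped study drug at an ED visit, footnote y says that no dose is given, so the postdose window does not apply.

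**The concern.** One window is tied to the dose and the other to a clock time fixed up to two years before. Nothing links the two, so whether they overlap for a given subject depends on when the Screening LP happened to be done. A subject who consents to the substudy later may have had an eligibility LP timed with no substudy in view, and that time cannot be changed.

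Where the windows do not overlap, the site has to miss one, and the protocol does not say which. If sites choose differently, CSF elenbecestat and CSF Aβ in the active arm are taken at uncontrolled times after the dose, which weakens the exposure-response work in Section 9.7.1.7.2. If the clock match is given up instead, variation in time of day is added to the changes from Screening in CSF Aβ, t-tau and p-tau, which are named biomarker endpoints in Section 9.7.1.1.3.

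**Working it through.** The plan gives no figure to reproduce, so the check is the overlap of the two windows.

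**Inputs from the protocol.** The postdose window is 4 to 8 h and the clock window is ±1 h (Table 5 footnote y, Table 9 footnote k). The dose is in the morning, at the clinic, after the predose sample (Section 9.4.5, Table 5 footnote w). No clock time is stated for the dose or for the Screening LP.

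**Assumptions.** A clinic dose at 07:00, 08:00 or 09:00. For the share affected only, Screening LPs spread evenly over 08:00 to 16:00.

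**Step 1: overlap.** Let D be the dose time, S the Screening LP time and L the on-treatment LP time.
- Postdose window: D+4 ≤ L ≤ D+8.
- Clock window: S−1 ≤ L ≤ S+1.
- A common L exists only if S+1 ≥ D+4 and S−1 ≤ D+8, that is, D+3 ≤ S ≤ D+9.

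**Step 2: workable Screening LP times, and share outside them.** Between 08:00 and 16:00 the upper limit D+9 (16:00, 17:00, 18:00) excludes nothing. The share outside is therefore (D+3−8)/8.

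| Dose D | Workable Screening LP | Share outside |
|---|---|---|
| 07:00 | 10:00–16:00 | 2/8 = 25% |
| 08:00 | 11:00–17:00 | 3/8 = 38% |
| 09:00 | 12:00–18:00 | 4/8 = 50% |

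**Step 3: the same rule read backwards.** The latest workable dose is S−3 h.

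| Screening LP | Latest dose |
|---|---|
| 08:00 | 05:00 |
| 09:00 | 06:00 |
| 10:00 | 07:00 |
| 11:00 | 08:00 |

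The first two are not practicable for a dose given at the clinic after a predose blood draw.

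**Step 4: size of the miss.** Take S = 09:00 and D = 08:00. Keeping the postdose window puts the LP at 12:00 at the earliest, 3 h from the Screening time. Keeping the clock window puts it at 10:00 at the latest, at most 2 h after the dose and not 4 to 8 h.

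**The case against.** The strongest reply is that this is no contradiction. The windows overlap for a six-hour span of Screening LP times, a site can read both footnotes before it schedules the Screening LP, and a laboratory manual that is not shown may help. That stands in part: a site that plans ahead can comply. It does not help subjects who join the substudy after the eligibility LP, and nothing in the protocol tells the site to plan ahead.

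Section 9.5.1.3.3 asks only for approximately the same time of day, and that sentence carries the later amendment tag (Amendment 05, against Amendment 01 in footnote y). This softens the conflict but does not settle it. Table 9 footnote k sits in an appendix itself marked as revised by Amendment 05 and still gives ±1 hour, and a 3-hour gap is hard to call approximate.

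A reader might infer more than the documents support:
- *That every morning Screening LP is unworkable.* It is not. No dose clock time is fixed, and the one-hour tolerance makes 10:00 workable with a 07:00 dose and 11:00 with an 08:00 dose.
- *That time of day is confounded with treatment.* Both randomised arms follow the same blinded schedule, so the mismatch falls on both and adds noise to the between-arm comparison.
- *That the fasting preference pushes Screening LPs into the morning.* The same sentences allow an LP 2 hours after a meal, and the protocol gives no distribution of LP times.

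The CSF substudy is also optional, its endpoints are tested without multiplicity adjustment (Section 9.7.1.7.3), and the PK/PD work is exploratory. All of that stands and limits the weight of the point.

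**Conclusion.** The point holds in a limited form. Two stated rules cannot in practice both be followed for subjects whose Screening LP was in the early or middle part of the morning. The exception is an ED visit after drug has stopped, when no dose is given. The condition D+3 h to D+9 h follows from the protocol's own figures and needs no assumption.

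The number of subjects affected cannot be derived from the protocol. The 25%, 38% and 50% rest on assumed dose times and an assumed even spread of LP times; they show a range and are not estimates. The protocol also gives no CSF concentration profile, so the effect of a shifted postdose time on CSF drug level or Aβ cannot be sized.

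The main loss is control of postdose sampling time in the active arm, which randomisation does not repair, with added noise in change from Screening. The primary endpoint (CDR-SB) and the key secondary endpoints (ADCOMS and amyloid PET) are not touched. It is a cheap improvement to a biomarker substudy.

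**What to change.** Reconcile Section 9.5.1.3.3, Table 4 footnote o, Table 5 footnote y and Table 9 footnote k so that:
- the Screening LP is scheduled relative to the site's planned clinic dosing time, such that both windows can later be met;
- the clock match is stated once, either with the ±1 hour limit or as approximate;
- the sponsor says which window prevails for subjects already screened outside the workable range. Which one, and at what hours, is for the sponsor to decide.

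Use the recorded LP clock time and time since dose in the CSF analyses, if the statistical analysis plan does not already do so.

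The cost is wording in three footnotes and one section. The downside is that fewer LPs may be done fasting, and some subjects already screened will lose one of the two matches whatever is decided.
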